9.2.2 Study population

Inclusion criteria:

- 1. At least one prescription for Tio+Olo (FDC or free combination) as a new initiation between 1st January 2014 and 31st December 2019.
- 2. Aged \geq 40 years on the index date;
- 3. At least one diagnosis of COPD at any time prior to or on the index date;
- 4. At least one year of continuous medical and health insurance plan prior to the index date will be required to allow for a look-back period for the covariates and identification of new use of the study drugs;
- 5. At least one record in the health insurance system database;

Exclusion criteria:

- 1. Any use of Tio+Olo in free or fixed form within one year prior to the index date;
- 2. Individuals with asthma, allergic rhinitis, lung cancer, interstitial lung disease, or lung transplant identified at any time prior to the index date;

Another cohort of patients using other LAMA/LABAs (FDC or free combination) will also be enrolled to collect the information of baseline characteristics to be compared with those of patients treated with Tio+Olo. The Inclusion/Exclusion criteria are similar with those of Tio+Olo, which include:

Inclusion criteria:

- 1. At least one prescription for LAMA+LABA (FDC or free combination) other than Tio/Olo as a new initiation between 1st January 2014 and 31st December 2019.
- 2. Aged \geq 40 years on the index date;
- 3. At least one diagnosis of COPD at any time prior to or on the index date;
- 4. At least one year of continuous medical and health insurance plan prior to the index date will be required to allow for a look-back period for the covariates and identification of new use of the study drugs;
- 5. At least one record in the health insurance system database.

Exclusion criteria:

- 1. Any use of LAMA+LABA in free or fixed form for one year prior to the index date;
- 2. Individuals with asthma, allergic rhinitis, lung cancer, interstitial lung disease, or lung

NIS Protocol Page 20 of 43 BI Study Number: 1237-0109 c38644780-01

Proprietary confidential information © 2022 Boehringer Ingelheim International GmbH or one or more of its affiliated companies

transplant identified at any time prior to the index date.

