6.3 STUDY POPULATION

For incident Tio/Olo combined inhaler cohort

• Inclusion criteria:

- 1. At least one prescription for Tio+Olo (fixed dose combination (FDC) or free combination) as a new initiation between 1st January 2014 and 31st December 2019 (the free combination will be defined as the prescriptions of the two compounds on the same day);
- 2. Aged ≥ 40 years on the index date (The first dispensing of Tio+Olo combined inhaler will be defined as the index date);
- 3. At least one diagnosis of COPD (ICD9: 491.x, 492.x, 496; ICD10: J41.x, J42, J43.x, J44.x) at any time prior to or on the index date;
- 4. At least one year of continuous medical and health insurance plan prior to the index date will be required to allow for a look-back period for the covariates and identification of new use of the study drugs;
- 5. At least one record in the health insurance system database.

• Exclusion criteria:

- 1. Any use of Tio+Olo in free or fixed form within one year prior to the index date. (the free combination will be defined as the prescriptions of the two compounds within 30 days);
- 2. Individuals with asthma, allergic rhinitis, lung cancer, interstitial lung disease, or lung transplant identified at any time prior to the index date.

Relevant ICD codes and procedure code are provided in the Annex.

Statistical and Epidemiological Analysis Plan (SEAP) for Non-Interventional Studies (NIS) Template c40431892-01 Page 7 of 38

Proprietary confidential information © 2022 Boehringer Ingelheim International GmbH or one or more of its affiliated companies

For other incident LAMA/LABAs combined inhaler cohort

Inclusion criteria:

- 1. At least one prescription for LAMA+LABA FDC (Vilanterol/Umeclidinium; Indacaterol /Glycopyrronium) or free combination (LABA: Salmeterol; Formoterol; Procaterol; Indacaterol; Olodaterol, LAMA: Tiotropium bromide; Glycopyrrolate; Umeclidinium) other than Tio/Olo as a new initiation between 1st January 2014 and 31st December 2019 (the free combination will be defined as the prescriptions of the two compounds on the same day);
- 2. Aged ≥ 40 years on the index date (The first dispensing of LAMA+LABA combined inhaler will be defined as the index date);
- 3. At least one diagnosis of COPD at any time prior to or on the index date;

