7.2.2 Secondary outcomes

These are not "outcomes" that occurred after the index date in most studies. These are analysis of baseline characteristics of patients who initiated Tio+Olo or other LAMA/LABA.

Basic characteristics:

• Sex

Statistical and Epidemiological Analysis Plan (SEAP) for Non-Interventional Studies (NIS) Template

c40431892-01 Page 12 of 38

Proprietary confidential information © 2022 Boehringer Ingelheim International GmbH or one or more of its affiliated companies

- Age
- Calendar year of cohort entry
- Season of index date (winter, Dec-Feb; spring, Mar-May; summer, Jun-Aug; fall, Sep-Nov)

Additional characteristics will be defined during the 1-year pre-index baseline period:

- Specific previous COPD treatments
 - > LAMA monotherapy
 - ➤ LABA monotherapy
 - ➤ ICS monotherapy
 - LAMA/ICS combination therapy on the same day
 - ➤ LAMA+LABA free combinations and fixed dose combination
- Use of other respiratory drugs
 - Mucolytics
 - > Theophylline
 - Short-acting beta-agonists
 - Short-acting muscarinic antagonists
- Previous acute COPD exacerbation (measured both 12 months and in the 30 days prior to cohort entry), categorized as 0, 1, or 2+.
 - ➤ All exacerbations (Moderate + Severe)
 - An outpatient visit with a diagnosis code for COPD in any field + a prescription for an oral corticosteroid or an antibiotic for respiratory infections (Moderate); prescriptions within 30 days of each other were considered as continuation of the initial exacerbation.
 - ➤ Hospitalizations or emergency room visits with a primary diagnosis for COPD (Severe); hospitalizations or emergency room visits within 30 days of each other were considered as continuation of the initial exacerbation.
- Hospitalizations caused by exacerbation of COPD in 12 months prior to index date:
 - \triangleright 0;
 - **>** 1;
 - >=2:
- All-cause hospitalizations in 12 months prior to index date;
- Comorbidities:
 - Cardiovascular disease
 - Cerebrovascular disease
 - Diabetes
 - Chronic kidney disease
 - Pneumonia
 - > Cancer
 - Cirrhosis
- Charlson Comorbidity Index (CCI)

Statistical and Epidemiological Analysis Plan (SEAP) for Non-Interventional Studies (NIS) Template c40431892-01 Page 13 of 38

Proprietary confidential information © 2022 Boehringer Ingelheim International GmbH or one or more of its affiliated companies

- History of medications dispensed in the 12 months before or on the index date will be identified from the pharmacy dispensing history:

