Appendix 1. Relevant ICD-9/10-CM code and procedure code

	ICD9	ICD10
For inclusion criteria		
COPD	491.x, 492.x, 496	J41.x, J42, J43.x, J44.x
For exclusion criteria		
Asthma	493.x	J45.x
Allergic rhinitis	477.x	J30.x
Lung cancer	162.x	C33.x, C34.x, C7A.090,
		D02.2
Interstitial lung disease	238.1, 500, 501, 502, 503,	J60, J61, J62.x, J63.x, J64,
	504, 505, 506.4, 508.1,	J65, J66.x, J68.4, J70.x (no
	508.8, 515, 516.x	70.2), J84.1x (no J84.114),
		J84.2, J84.3, J84.89, J84.9,
		J94.1

Procedure codes	Content
68037A	Lung transplantation
68037B	Lung transplantation - Unilateral lung
68047B	Lung transplantation - bilateral sequential or en bloc double lung

Statistical and Epidemiological Analysis Plan (SEAP) for Non-Interventional Studies (NIS) Template

c40431892-01 Page 29 of 38

Proprietary confidential information © 2022 Boehringer Ingelheim International GmbH or one or more of its affiliated companies

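### In both cohorts a COPD code on the index date counts for entry, but an exclusion diagnosis coded on that same date does not exclude

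*SAP*

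**What the plan says.** SAP 6.3 sets eligibility for the Tio/Olo cohort and the other LAMA/LABA cohort in parallel.

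- **COPD (inclusion 3).** For Tio/Olo, a listed code counts "at any time prior to or on the index date". For the comparator the rule is "At least one diagnosis of COPD at any time prior to or on the index date".
- **Exclusion diagnoses (exclusion 2).** In both cohorts the plan removes "Individuals with asthma, allergic rhinitis, lung cancer, interstitial lung disease, or lung transplant identified at any time prior to the index date".
- **Index date.** For Tio/Olo: "The first dispensing of Tio+Olo combined inhaler will be defined as the index date". The comparator has the matching definition.

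Protocol 9.2.2 and the protocol abstract have the same pair of windows. Exclusion 2 there ends "lung cancer, interstitial lung disease, or lung transplant identified at any time prior to the index date". SAP Appendix 1 lists the diagnosis codes under "For exclusion criteria", with lung transplant procedure codes below them, and attaches no timing rule to either.

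**The concern.** COPD and a competing diagnosis can first be coded on the same day, and treatment can be dispensed that day. The plan then uses the first code and ignores the second. Claims codes are the only means of separating these conditions here, because SAP 6.1 states that spirometry and smoking data are not available.

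Patients who stay in for this reason contribute to the primary rates. SAP Appendix 3 defines a moderate COPD exacerbation as an outpatient COPD code plus an oral corticosteroid or a listed antibiotic. An enrolled patient who carries both a COPD and an asthma code could meet that definition through treatment of asthma. Lung cancer bears on all-cause mortality, which is also an outcome. The same patients enter the baseline comparison that forms the secondary objective.

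**Working it through.** No sample size or power figure is at issue. The check is a comparison of the text, followed by a statement of what would be needed to size the effect.

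**1. Does the exclusion window include the index day?** The plan names that day when it wants it counted. It does so for the COPD diagnosis ("at any time prior to or on the index date") and for medication history ("History of medications dispensed in the 12 months before or on the index date", SAP 7.2.2). Exclusion 2 does not name it, so the consistent reading is that the index day is outside the window. No readable section extends it.

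**2. Apply the rules.** Take a patient aged 40 or over with a COPD code on or before the index date, one year of prior cover, no qualifying prior use, and a single first exclusion code, say asthma.

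| Date of first asthma code | Result as written | Result if the index day were included |
|---|---|---|
| Before the first dispensing, including an initiating visit dated earlier | Excluded | Excluded |
| Same date as the first dispensing | **Enrolled** | Excluded |
| After the first dispensing | Enrolled | Enrolled |

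Only the middle row changes, and it is the same in both cohorts.

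**3. Would including the index day use future information or remove outcomes?** No to both. The index day is cohort entry, and the plan already uses COPD codes and dispensings from that day. None of the five exclusion conditions is on the adverse event list in SAP 7.2.1.

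**4. Size.** Let s be the share of person-time from index-day cases and k the ratio of their event rate to that of everyone else. Then

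pooled rate ÷ rate in the others = (1 − s) + s·k = 1 + s(k − 1).

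The documents give neither s nor k, so the effect cannot be estimated. For scale, s(k − 1) can be set against the planned precision in Protocol Table 1. That table reproduces as Poisson quantiles over 4,000 × 3 = 12,000 patient-years. For pneumonia, 0.0469 × 12,000 = 562.8 expected events gives 4.308 to 5.083, as printed. The relative half-widths are:

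- COPD exacerbation: (56.758 − 54.092) / 2 / 55.42 = 2.4%
- Pneumonia: (5.083 − 4.308) / 2 / 4.69 = 8.3%
- Arrhythmia: (2.067 − 1.583) / 2 / 1.82 = 13.3%
- Supraventricular tachycardia: (1.358 − 0.975) / 2 / 1.16 = 16.5%

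If k were 2, which is purely an illustration, s(k − 1) = s. Index-day cases would then have to supply 2.4% of person-time to shift the exacerbation rate by its planned half-width, and 8.3% to do so for pneumonia. Follow-up ends at discontinuation, so 4,000 patients will give fewer than 12,000 patient-years and the real margins will be wider.

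**The case against.** The strongest reply is that the difference may be intended. COPD is the condition being treated, so accepting its code on the day of first dispensing is natural. The other exclusion is also pre-index, and most covariates are taken from a pre-index baseline. An asthma code beside a COPD code on the first day may be a rule-out diagnosis, and excluding on it could remove genuine COPD patients.

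Part of this stands: some patients removed by the change would have COPD alone. But it does not separate the index day from the day before. Appendix 1 has no confirmation requirement, so one earlier code already excludes. By contrast, Appendix 4 requires an inpatient code or repeated outpatient codes for most comorbidities. Exclusion 1 has to stop before the index day because use on that day is the initiation itself; exclusion 2 has no such constraint.

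Other limits stand in full.

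- A reader might infer that anyone first coded with asthma or lung cancer at the initiating visit gets in. That holds only if the code and the first dispensing share a date. The documents do not say which claim date is used.
- A reader might call these patients wrongly enrolled. Under the rules as written they are eligible, and the documents give no rationale for exclusion 2.
- A reader might put a figure on the bias. If 1–5% of patients were affected with a doubled rate, that would be 40–200 of 4,000 and a rise of about 1–5%. Neither input has a source. One ratio cannot serve five different conditions, and a headcount share is not the person-time share that the formula needs.
- A reader might expect the leak to distort the comparison between cohorts. The rule is the same in both, and nothing shows that one has more newly diagnosed patients.

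The flow chart in SAP Figure 1 was not available to read. If it carries another window, the text still has to be brought into line with it.

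**Conclusion.** The inconsistency is real and appears in both cohorts and both documents. As written, a first exclusion code dated on the day of first dispensing leaves the patient enrolled, and the plan does not say why. This rests on reading the exclusion window as stopping short of the index day, which the plan's own usage elsewhere supports.

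Bias in the primary rates or in the baseline comparison is not shown. The number of patients affected is unknown and may be small. The point should be corrected because it decides who enters the primary analysis, the change is cheap, and two analysts should reach the same cohort (SAP 11 has a second analyst review or repeat the work). It does not threaten the study.

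**What to change.** In exclusion 2, for both cohorts, in Protocol 9.2.2 (and its abstract) and SAP 6.3, insert *or on* after *prior to*, so that the window matches inclusion 3. In SAP Figure 1, report the number removed by index-day codes, separately for each cohort. SAP 9.2 and 9.3 already use that figure to report other removals, and the count would replace speculation about size with data.

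The cost is one phrase in two documents and a slightly smaller cohort. Some of those removed may have only a rule-out code on that day, which is already true of patients removed for earlier codes.

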6.4 STUDY VISITS

Not applicable.

7. VARIABLES

7.1 EXPOSURES

Exposure of this study is defined as new initiation of Tio/Olo or other LAMA/LABA inhaler (FDC or free combination) during the study period. The free form will be defined as the prescriptions of the two compounds on the same day. Drug codes of interest are provided in the Annex.

7.2 OUTCOMES

7.2.1 Primary outcomes

➤ Incidence rate of adverse events in patients with COPD treated with Tio+Olo

List of adverse events:

For acute, potentially recurrent events, including COPD exacerbations listed below, all subjects will be evaluated, regardless of whether such events occurred during the one-year baseline period.

- Respiratory tract disorders
 - 1. Nasopharyngitis
 - 2. Pneumonia
 - 3. COPD exacerbation
- Gastrointestinal disorders
 - 1. Constipation
 - 2. Diarrhoea
- Urinary disorders
 - 1. Urinary retention
 - 2. Urinary tract infection
- Immune system
 - 1. Urticaria

Statistical and Epidemiological Analysis Plan (SEAP) for Non-Interventional Studies (NIS) Template

c40431892-01 Page 10 of 38

Proprietary confidential information © 2022 Boehringer Ingelheim International GmbH or one or more of its affiliated companies

2. Rash

For chronic conditions listed below, subjects who had diagnosis of the condition during the one-year baseline period will be excluded from the incidence of adverse event analysis.

- Cardiovascular disorders
 - 1. Arrhythmia
 - 2. Myocardial ischemia
 - 3. Supraventricular tachycardia
- Ophthalmic disorders
 - 1. Glaucoma
- Serious Adverse Event (SAE)
 - 1. Nonfatal myocardial infarction
 - 2. Nonfatal stroke (hemorrhagic stroke, ischemic stroke and acute cerebrovascular disease)

Lastly, all-cause mortality, a serious adverse event, will be evaluated.

Relevant ICD codes and operational definition are provided in the Annex.

[figure not shown]
For the analysis of the primary outcome, individuals will be followed up from the index date until the earliest of the following

- 1) Outcome of interest
- 2) disenrollment;
- 3) the end of the study period;
- 4) death;
- 5) discontinuation of the index drug use as a lapse of 45 days without subsequent prescription;
- 6) adding ICS mono on top of Tio/Olo.

Statistical and Epidemiological Analysis Plan (SEAP) for Non-Interventional Studies (NIS) Template

c40431892-01 Page 11 of 38

Proprietary confidential information © 2022 Boehringer Ingelheim International GmbH or one or more of its affiliated companies

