10. DATA ANALYSIS

10.1 MAIN ANALYSIS

All variables, including patient characteristics, baseline measures, and outcomes, will be analyzed descriptively.

- For all analyses, variables will be reported as follows: Continuous variables (e.g., age) will be presented as means (with standard deviation, SD) and/or medians (with interquartile range, IQR), minimum, maximum.
- Categorical variables (e.g., sex) will be presented as absolute and relative frequencies.

We will first describe formation of the study cohort. Patient characteristics at baseline will be described using standard descriptive statistics. Absolute standardized differences (ASDs) will be used to compare the characteristics between the two groups, in which a >0.1 ASD indicates a meaningful difference.

As an objective of the study was to compare the clinical attributes of patients in each study group. The standardized difference will be used as a parameter to quantify the between-group differences for each clinical attribute. This is metric is commonly used in studies utilizing

Statistical and Epidemiological Analysis Plan (SEAP) for Non-Interventional Studies (NIS) Template

c40431892-01 Page 15 of 38

Proprietary confidential information © 2022 Boehringer Ingelheim International GmbH or one or more of its affiliated companies

secondary health data, in which a standardized difference of larger than 0.1 indicates a meaningful difference with respect to the clinical attribute between the two study groups.

For the analysis of primary outcome, the incidence rates of AEs during entire follow-up period will be calculated based on the following formula:

(Total number of patients in the Tio+Olo cohort experiencing an event of interest for the first time during the given time period) / (Total person-time at risk from current use of Tio+Olo during the given period)

[figure not shown]
Number of at-risk patients will be defined for specific adverse outcome of interest, taking into account whether it is a chronic condition for which patients with a prevalent condition are not considered at risk.

For the analysis of the primary outcome, individuals will be followed up from the index date until the earliest of the following

- 1) Outcome of interest
- 2) disenrollment;
- 3) the end of the study period;
- 4) death;
- 5) discontinuation of the index drug use as a lapse of 45 days without subsequent prescription;
- 6) adding ICS mono on top of Tio/Olo.

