Appendix 3. ICD codes and operational definition of adverse events

	Adverse events	ICD codes	Operational definition
1	Nasopharyngitis	ICD9: 472.2, 460 ICD10: J31.1, J00	Inpatient or outpatient (including ER visit) diagnosis.
2	Pneumonia	ICD9: 480-486, 487.0 ICD10: J10.0, J11.0, J12- J18,	 Primary inpatient diagnosis Inpatient diagnosis.
3	Moderate COPD exacerbation	ICD9: 491.x, 492.x, 496 ICD10: J41.x, J42, J43.x, J44.x	Outpatient diagnosis plus a prescription for oral corticosteroid or antibiotic for respiratory infection
4	Severe COPD exacerbation	ICD9: 491.x, 492.x, 496 ICD10: J41.x, J42, J43.x, J44.x	Inpatient or ER visits with a primary diagnosis.
5	Arrhythmia	ICD9: 427.x ICD10: I47.x, I48.x, I49.x	Inpatient or outpatient (including ER visit) diagnosis.
6	Myocardial ischemia	ICD9: 410.x, 411.x, 413.x ICD10: I20.x, I21.x, I22.x, I23.x, I24.x	Inpatient or outpatient (including ER visit) diagnosis.
7	Supraventricular tachycardia	ICD9: 427.0 ICD10: I47.1	Inpatient or outpatient (including ER visit) diagnosis.
8	Constipation	ICD9: 564.0, 564.00, 564.09 ICD10: K59.0, K59.00, K59.09	Inpatient or outpatient (including ER visit) diagnosis.
9	Diarrhoea	ICD9: 787.91 ICD10: R19.7	Inpatient or outpatient (including ER visit) diagnosis.
10	Urinary retention	ICD9: 788.2, 788.20, 788.29 ICD10: R33.x	Inpatient or outpatient (including ER visit) diagnosis.
11	Urinary tract infection	ICD9: 590, 595, 601, 604 ICD10: N10, N12, N15.1, N30.0, N30.8, N30.9, N41.0, N41.2, N41.3, N39.0	 Primary inpatient diagnosis Inpatient diagnosis. Either inpatient diagnosis or at least 2 outpatients (including ER visit) diagnosis; diagnostic interval within 30 days.
12	Urticaria	ICD9: 708.x ICD10: L50.x	Inpatient or outpatient (including ER visit) diagnosis.
13	Rash	ICD9: 782.1 ICD10: R21	Inpatient or outpatient (including ER visit) diagnosis.

Statistical and Epidemiological Analysis Plan (SEAP) for Non-Interventional Studies (NIS) Template

c40431892-01 Page 31 of 38

14	Glaucoma	ICD9: 365.x	Inpatient or outpatient
		ICD10: H40.x	(including ER visit) diagnosis
			from ophthalmologist.
15	Nonfatal myocardial	ICD9: 410.x, 411.x	1. Primary inpatient diagnosis
	infarction	ICD10: I21.x, I22.x, I23.x	+ hospital discharge
			without death certificates
			2. Inpatient diagnosis +
			hospital discharge without
			death certificates
16	Nonfatal hemorrhagic stroke	ICD9: 430, 431, 432.x	1. Primary inpatient diagnosis
		ICD10: 160.x, 161.x, 162.x	+ hospital discharge
			without death certificates

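### Follow-up starts on the day of first dispensing and no readable rule excludes that day's events, so an exacerbation treated at the initiating visit counts as a first on-drug event

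*SAP*

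**What the plan says.** **Start and end of follow-up.** SAP 7.2.1 and 10.1 use the same sentence: "individuals will be followed up from the index date until the earliest of the following". The first item in the list that follows is the outcome itself. Protocol 9.7.1 also starts at the index date. SAP 6.3 fixes that date: "The first dispensing of Tio+Olo combined inhaler will be defined as the index date".

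**The rate.** The numerator in SAP 10.1 is the number of patients with a first event in the period. The denominator is "Total person-time at risk from current use of Tio+Olo during the given period".

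**Prior events.** For acute, potentially recurrent events, SAP 7.2.1 says that "all subjects will be evaluated, regardless of whether such events occurred during the one-year baseline period". For chronic conditions, a diagnosis in the baseline year removes the patient. The index day is not mentioned in either rule.

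**Outcome definition.** SAP Appendix 3 defines a moderate exacerbation as "Outpatient diagnosis plus a prescription for oral corticosteroid or antibiotic for respiratory infection". One visit can meet this, and there is no date condition relative to the index date. The SAP does not say whether inpatient events are dated by admission or by discharge.

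**Continuation of an episode.** For the baseline covariate only, SAP 7.2.2 says that "prescriptions within 30 days of each other were considered as continuation of the initial exacerbation", with a matching rule for severe episodes ("hospitalizations or emergency room visits within 30 days of each other were considered as continuation of the initial exacerbation"). Appendix 3 has no such rule for the exacerbation outcome.

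**Index day as baseline.** SAP 6.3 accepts a COPD diagnosis made on the index date as qualifying. The medication history in SAP 7.2.2, which includes antibiotics, also takes in dispensings on the index date.

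**The concern.** A patient may start the drug at the same visit at which an exacerbation is treated. That exacerbation came before the first dose, yet under the readable rules it is a first event on the drug. Because follow-up stops at the outcome, the patient adds one event and almost no person-time.

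The same visit can also be used twice. Its COPD code can qualify the patient for the cohort and supply half of the outcome. Its antibiotic can be baseline history and supply the other half.

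The primary result is an absolute rate in one cohort, so no comparator cancels the error. COPD exacerbation has the highest expected rate of the four events in Protocol Table 1. SAP section 11 has a second analyst review or repeat the analysis. Two analysts who treat day 0 differently could both claim to follow the text and obtain different rates.

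**Working it through.** **1. The Protocol's own figure.** Protocol 9.5 assumes 4,000 patients, uniform follow-up of 0 to 6 years (mean 3) and an exacerbation rate of 55.42 per 100 person-years.
- Person-years: 4,000 × 3 = 12,000. Expected events: 0.5542 × 12,000 = 6,650.4.
- The 2.5% and 97.5% Poisson quantiles divided by 12,000 give 54.092 to 56.758, which matches Table 1. The half-width is (56.758 − 54.092)/2 = 1.33.

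That interval lets every patient contribute full time. The SAP rate stops at the first event, so the person-time below is smaller.

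**2. Direction.** Let a share p of patients have an index-day event. Let P0 and E0 be the later event probability and mean time at risk of the other patients, and P1 and E1 those of the index-day patients if followed on.
- Events: p + (1−p)P0 when day 0 counts, against pP1 + (1−p)P0 when it does not. The first is never smaller.
- Time: (1−p)E0 when day 0 counts, against pE1 + (1−p)E0. The first is never larger.

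The rate therefore goes up, whatever the later hazard of the index-day patients.

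**3. Size (illustration).** From the Protocol: h = 0.5542 per year and uniform 0 to 6 years. Assumed: p, and a discontinuation hazard d of 0 or 1 per year. All patients have the same later hazard here.
- E = ∫₀⁶ (1 − t/6) exp(−(h+d)t) dt and P = hE.
- d = 0: E = 1.281 years (5,125 person-years), P = 0.710.
- d = 1: E = 0.574 years (2,298 person-years), P = 0.318.
- Rate with day 0 counted = [p + (1−p)P]/[(1−p)E] = h + p/[(1−p)E].
- Half-width = 1.96 √(4,000P)/(4,000E), which is 2.04 (d = 0) or 3.04 (d = 1) per 100 person-years.

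Example, p = 5%, d = 0: 0.5542 + 0.05/(0.95 × 1.281) = 0.595.

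| Assumed share p | Rate per 100 PY, d = 0 | Rate per 100 PY, d = 1 |
|---|---|---|
| 0.5% | 55.81 | 56.29 |
| 1% | 56.21 | 57.18 |
| 2% | 57.01 | 58.97 |
| 5% | 59.53 | 64.58 |

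**4. Sensitivity to the assumptions.**
- Later hazard doubled in index-day patients, with the base hazard re-solved so that the corrected rate stays 55.42: shares of 1%, 2% and 5% give 55.87, 56.34 and 57.80 (d = 0), or 56.75, 58.12 and 62.41 (d = 1).
- One day of person-time credited per index-day event: at p = 5% the rates are 59.52 and 64.57, so this hardly matters.
- The shift p/[(1−p)E] grows as time on drug gets shorter.

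The model treats exacerbation as one combined outcome. SAP Table 2 reports moderate and severe in separate rows, and neither row is computed here.

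**The case against.** **Silence is not proof.** Parts of the plan cannot be read in the public copy: figures in SAP 6.3, 7.2.1 and 10.1, SAP page 16, the annex pages 23 to 27, SAP 10.2 and Protocol 9.7.2. A day-0 rule could sit there. This stands. The point is limited to the readable text, and a reader should not infer that the plan has no rule at all.

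**The washout sentence says nothing about day 0.** This is also right. A reader might take "all subjects will be evaluated, regardless of whether such events occurred during the one-year baseline period" as a decision to count index-day events. It concerns history in the baseline year, and ignoring that history is sensible for recurrent events. The start-of-follow-up sentence carries the point.

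**Other wording points away from counting day 0.** SAP 7.2.2 speaks of outcomes "that occurred after the index date in most studies", the denominator is time on current use, and index-day antibiotics are filed as history. None of these tells a programmer to drop an index-day outcome. The last leaves the same dispensing eligible for both sides.

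**The size is assumed.** This stands. No document gives the index-day share or the time on drug. The half-widths of 2.04 and 3.04 come from the illustration and not from Protocol Table 1, so shifts expressed in half-widths depend on the benchmark chosen.

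**Dropping day 0 could hide true first-day reactions.** In a post-authorization safety study this matters for outcomes such as rash, urticaria or arrhythmia. It stands, and the fix keeps the day-0-inclusive rate in the report.

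**The analysis is descriptive.** No readable test or threshold depends on the rate. But the rate is the primary result, and the readable rule makes it worse in a known direction.

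**Conclusion.** The point holds for index-day events. Followed literally, the readable plan counts an exacerbation treated at the initiating visit as a first on-drug event with 0 to 1 day of person-time, which biases the absolute rate upward.

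The direction needs no assumption about those patients' later hazard. The size is unknown. With assumed shares of 1% to 5%, the illustration gives 56.2 to 59.5 per 100 person-years without discontinuation and 57.2 to 64.6 with a discontinuation hazard of 1 per year, against 55.42. The shifts are smaller if index-day patients later have a higher hazard. At a share of 0.5% the shift is 0.4 to 0.9 per 100 person-years.

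Two stronger readings are not supported. A reader might infer that repeat contacts for an episode begun before the index date also inflate the rate. The text leaves them uncontrolled, but neither their size nor their direction has been shown. A reader might also infer a known, large bias in every listed outcome. The gap in the rule is common to the non-fatal outcomes, but only exacerbation is illustrated, and only under assumptions.

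This should be fixed before the analysis is programmed. Confidence is medium because of the unreadable text.

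**What to change.** Unless a rule already exists in text that cannot be read, write the following into SAP 7.2.1, 10.1 and Appendix 3:
- Start time at risk on the day after the index date for COPD exacerbation and the other non-fatal outcomes.
- Date inpatient events by admission.
- Treat index-day diagnoses as baseline. For the chronic conditions, such a patient is then prevalent and not at risk.
- Keep deaths counted from the index date.
- For every outcome, also report the number of index-day events and the rate with day 0 included, so that possible first-day reactions stay visible and the true size of the effect is known.

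Optional sensitivity analysis, for exacerbation only: apply the SAP's existing 30-day continuation rule across the index date with a fixed window, and start time at risk when the window closes.

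**Cost.** The main change is SAP wording and one date condition in the program. It removes one day per patient, 4,000/365.25 = about 11 person-years, and moves a few true first-day events out of the main rate. The sensitivity analysis also loses some true early events. If 10% of patients were affected (assumed), a fixed window costs at most 400 × 30/365.25 = about 33 person-years, or 0.6% of 5,125 and 1.4% of 2,298.
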